##### **Secondary endpoints**

- Quality of life evaluated through the "Minnesota Questionnaire for People with Heart Failure" (Change in the value of the questionnaire scale at 3 months)
- Patient-Reported Self-Care Behavior Scale Measures (EHFScB Scale) (Change in Questionnaire Scale Value at 3 Months)
- Patient adherence to treatment and medication intake (SMAQ Simplified Medication Adherence Questionnaire) (Change in the value of the questionnaire scale at 3 months)
- Death from cardiovascular (CV) causes (Total number of patients who died in 3 months)

- Mortality from any cause (Total number of patients who died in 3 months)
- Acute HF decompensation (first and recurrent) during the follow-up period (Number of total decompensations in 3 months).

An acute decompensation of HF is defined as a new episode of symptoms and signs that requires intravenous decongestive treatment or increased oral diuretics either on an outpatient basis (e.g., day or home hospitalization for HF) or at home, emergency department or requiring an unplanned hospital admission.

- Hospital readmission due to HF decompensation (Total number of hospitalizations in 3 months)
- Hospital readmission for CV causes (Total number of hospitalizations in 3 months)
- Visits to the emergency room due to HF decompensation (Total number of visits to the emergency room in 3 months)
- Visits to the emergency room for CV causes (Total number of visits to the emergency room in 3 months)
- Medical care costs (Sum of costs for medication consumption, hospitalization, emergency care and medical transportation in 3 months)

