### 7.2.3 Withdrawal criteria

Subjects will be informed that they can withdraw from the research whenever they wish, without this affecting in any way their subsequent medical care.

Complete withdrawal of consent for research means that the subject no longer wishes to use the investigational product and is unwilling or unable to continue participation in the research. Any subject may withdraw full consent to participate in the research at any time during the research. The investigator will discuss with the subject the most appropriate way to withdraw to ensure their health.

Every effort should be made to complete and report observations as widely as possible up to the date of withdrawal. All information must be included in the corresponding data collection notebooks.

The withdrawal criteria established for clinical research are as follows:

- Disease progression
- Withdrawal of consent or desire to terminate treatment or investigational product or failure to cooperate with research requirements
- Toxicity, adverse event, or intercurrent illnesses, in the opinion of the investigator, that justify discontinuation of treatment or investigational product
- Decision of the principal investigator, whether withdrawal is necessary to safeguard the interests of the patient
- Patient death
- New exclusion criteria clinically relevant to participants and affecting their safety
- Failure to comply with or significant deviation from the clinical research plan

If the participant withdraws from the study, their data will be automatically anonymized by the platform at the end of the study. This anonymization is not carried out if the participant gives explicit consent. The withdrawn participant will receive standard follow-up care designated by their respective medical professional.

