## 8 Design and statistical analysis

### 8.1 Methodology and analysis

Specific subgroup analyzes will be performed based on the different baseline data and risk factors available for the project. We will also test interactions between each pair of subgroups and the main effect of treatment.

Independent t tests or Mann-Whitney U tests will be used to compare the questionnaire scores based on the distribution of the data, whether normally distributed or not, respectively.

The incidence of secondary endpoint events in the two study groups will be described using Kaplan-Meier survival curves, which will be compared using the log-rank test. The hazard ratio will also be obtained using Cox proportional hazards regression models comparing the TM and UC groups. The time of each event will be calculated from the day of registration. We will compare the number of readmissions and days of hospitalization between the two groups using the Wilcoxon rank sum test.

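### Three secondary endpoints defined as 3-month event totals have no count or recurrent-event analysis in section 8.1, only Kaplan-Meier, log-rank and Cox

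*Combined protocol and SAP*

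**What the plan says.** Section 7.1.3 lists these secondary endpoints, each as a total:

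- "Acute HF decompensation (first and recurrent) during the follow-up period (Number of total decompensations in 3 months"
- "Visits to the emergency room due to HF decompensation (Total number of visits to the emergency room in 3 months"
- CV-related emergency attendances, likewise counted as a 3-month total

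HF and CV readmissions are also defined there as 3-month totals. The two mortality endpoints are counts of patients.

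Section 8.1 says of events: "The incidence of secondary endpoint events in the two study groups will be described using Kaplan-Meier survival curves", compared by log-rank, with a hazard ratio from Cox regression. It adds: "The time of each event will be calculated from the day of registration". The only count comparison is this: "We will compare the number of readmissions and days of hospitalization between the two groups using the Wilcoxon rank sum test". The t test or Mann-Whitney sentence covers questionnaire scores only.

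Table 1 (section 9.1) collects the number and dates of clinical events in both arms.

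On follow-up, section 7.2.3 lists "Disease progression" among the withdrawal criteria and asks that "Every effort should be made to complete and report observations as widely as possible up to the date of withdrawal". Section 8.1 does not say how time at risk is ended by withdrawal or death.

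**The concern.** The endpoint and the method answer different questions. A total that explicitly includes recurrent episodes asks how many events each arm has. Kaplan-Meier, log-rank and Cox, with one event time per patient, ask how soon the first event comes. A second or third decompensation within the 3 months then has no influence on the result.

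This matters because preventing exacerbations is a secondary objective (section 6.2), and section 7.1.2 chose the 3-month window because relapse is likely then. The plan also treats similar endpoints differently: readmission totals get a count test and these three do not. If the handling of repeat events stays open until data are seen, the analyst can choose among analyses that give different answers.

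**Working it through.** **1. Endpoints set against methods**

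| Secondary endpoint (7.1.3) | Defined as | Method in 8.1 | Count method? |
|---|---|---|---|
| Acute HF decompensation | total, including recurrent | KM, log-rank, Cox | no |
| HF emergency visits | total | KM, log-rank, Cox | no |
| CV emergency visits | total | KM, log-rank, Cox | no |
| HF and CV readmissions | totals | KM, log-rank, Cox, and Wilcoxon on number | yes (test only) |
| CV and all-cause death | patients | KM, log-rank, Cox | not needed |

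No section names a Poisson, negative binomial or other recurrent-event model.

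**2. The plan's own figure.** The only computed figure is N = 253 (section 7.1.4), for a 5-point MLHF difference at alpha 0.05 and 80% power. No SD is given. Two-sided and without dropout it implies SD = 5 × √(126.5/2) / (1.960 + 0.842) ≈ 14.2. It has no bearing on the event endpoints beyond giving about 126 per arm.

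**3. Share of events after the first.** The documents give no event rates, so these are assumptions: usual-care (UC) mean m = 0.2 to 1.0 events per patient over 3 months, and dispersion k = 0 to 2 (gamma-Poisson counts).

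Share = 1 − [1 − (1 + km)^(−1/k)] / m; for k = 0, 1 − [1 − exp(−m)] / m.

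| m | k = 0 | 0.5 | 1 | 2 |
|---|---|---|---|---|
| 0.2 | 0.09 | 0.13 | 0.17 | 0.23 |
| 0.5 | 0.21 | 0.28 | 0.33 | 0.41 |
| 0.8 | 0.31 | 0.39 | 0.44 | 0.53 |
| 1.0 | 0.37 | 0.44 | 0.50 | 0.58 |

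Example: m = 1, k = 2 gives 3^(−1/2) = 0.58.

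**4. Why the hazard ratio drifts.** With constant rates, rate ratio R, no deaths and time t as a fraction of 3 months, the first-event hazard ratio at t is R(1 + kmt) / (1 + kRmt). It starts at R. At day 90 with R = 0.60:

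- m = 0.2, k = 0.5: 0.60 × 1.10/1.06 = 0.62
- m = 0.5, k = 1: 0.60 × 1.50/1.30 = 0.69
- m = 1.0, k = 2: 0.60 × 3.0/2.2 = 0.82

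Only with k = 0 does it stay at 0.60.

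**5. Simulation.** 126 per arm, gamma frailty shared by events and death, two-sided 5%, no covariate adjustment, 5,000 trials, true rate ratio 0.60. Power (%) is at 7% deaths; hazard ratios span 3% to 12% deaths.

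| m, k | Log-rank | Negative binomial | Gain | Mean first-event HR |
|---|---|---|---|---|
| 0.2, 0.5 | 28.6 | 30.5 | 1.9 | 0.60 |
| 0.5, 1 | 45.3 | 55.9 | 10.6 | 0.63–0.64 |
| 0.8, 1 | 51.6 | 68.1 | 16.5 | 0.65–0.66 |
| 1.0, 0.5 | 66.8 | 84.6 | 17.8 | 0.64 |
| 1.0, 2 | 38.1 | 59.6 | 21.5 | 0.70–0.71 |

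The negative binomial rate ratio was 0.588 to 0.597 throughout. Moving deaths from 3% to 12% changed power by at most 3 points. A second simulation of the first, second and last settings gave 29 to 30, 46 to 57 and 37 to 60.

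At a true ratio of 0.70 and 7% deaths, the gain ran from 0.3 (17.3 to 17.6) to 18.0 points (39.1 to 57.1). The first-event hazard ratio was 0.70 to 0.78 and the negative binomial ratio 0.69 to 0.70.

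Under no effect (10,000 trials, four settings), log-rank rejected in 4.6% to 5.2% of trials and negative binomial in 4.4% to 5.5%.

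**The case against.** **Time to first event is a legitimate analysis.** It is: the test keeps its level, and if patients do not differ in underlying risk the hazard ratio equals the rate ratio. That supports keeping it as a secondary view. It does not make it an estimate of a total that includes recurrences.

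**The event rates are assumed, and at low rates little changes.** This stands. At a mean of 0.2 the hazard ratio is 0.60 against about 0.59, and the power gain is 2 points or less. Of the ten settings run at 7% deaths, one reaches 80% power under negative binomial.

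**The timing sentence may mean that repeats are used.** It only fixes the time origin. A reader might go further and infer that every event becomes an independent row, so that type I error is inflated. Section 8.1 describes no such analysis, and that charge is not made here.

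**Wilcoxon already covers part of this.** Decompensations that lead to admission reach it as readmissions; those managed at home, as an outpatient or in the emergency department do not. Nor should a reader infer that the readmission totals are properly estimated: Wilcoxon tests but gives no rate, so no event total in 8.1 has a planned rate estimate.

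**Withdrawal for disease progression.** A reader might infer a known bias. The documents do not support that: section 7.2.3 asks for data up to withdrawal, section 7.4 requires each readmission, death and emergency visit to be reported in both arms, and section 14.4.7 continues adverse-event follow-up after safety withdrawals. Nothing suggests that the precipitating event goes unrecorded, or that recording differs by arm.

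**Episodes treated only with more oral diuretics.** A reader might infer that these are not captured. Diuretic changes are in fact recorded in both arms (section 7.4 and Table 1). What remains is a labelling gap: section 7.4 names a non-fatal HF event for UC only, and the event list in Table 1 has no label for such an episode.

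**Conclusion.** The point holds for three secondary endpoints: HF decompensations, HF emergency visits and CV emergency visits. As written, section 8.1 gives them no estimate of the totals that section 7.1.3 defines. The mismatch is a matter of text and rests on no assumed figure, apart from reading Kaplan-Meier, log-rank and Cox in their usual one-event-per-patient form.

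Its size does rest on assumptions. With UC means of 0.2 to 1.0 and dispersion 0 to 2, 9% to 58% of UC events would be ignored. A true rate ratio of 0.60 would appear as a hazard ratio of about 0.60 to 0.71, and about 0 to 22 power points would be lost. The larger figures need frequent and unevenly spread events.

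This is a gap in what is estimated, not an invalid test. A reader might infer that the main result or the sample size is in doubt. Neither is: both concern the questionnaire endpoints.

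**What to change.** In section 8.1:

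1. Analyse the three totals by negative binomial regression, with log time at risk (registration to death, withdrawal or day 90) as offset. Report the rate ratio with its 95% CI. Adjust for the covariates used in the adaptive randomisation; section 7.3.1 does not name them, so list them.
2. Label Kaplan-Meier, log-rank and Cox for these three endpoints as supportive time-to-first-event analyses. Keep them for the death endpoints.
3. Report deaths and withdrawals, by arm and reason, beside each rate ratio, since either may be related to outcome.

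For consistency, the same model may be reported for HF and CV readmissions beside the planned Wilcoxon test.

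Side note: reconcile the UC and TM text of section 7.4 with the event list in Table 1, so that both arms record decompensations, including those treated only with increased oral diuretics, in the same way. No change to any clinical or withdrawal rule is implied.

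The cost is SAP wording and minor programming. Emergency-visit numbers and dates are already collected in both arms. The downside is that power hardly improves if event rates turn out low.

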#### 7.1.4 Sample calculation

The sample calculation has been made based on the fact that a change of 5 points on the scale of the Minnesota Questionnaire for People with Heart Failure (MLHF questionnaire) between the control group and the experimental group (telemonitored) is clinically significant. (Rector, n.d.). Assuming an alpha risk = 0.05 and a beta error of 20%, we need to recruit a total of 253 participants divided into a control group and an experimental group.

## 7.2 Subject selection

The target population includes patients recently decompensated by Heart Failure (HF).

All recruited subjects will meet the inclusion criteria and none of the exclusion criteria and will provide written informed consent.

#### 7.2.1 Inclusion criteria

- Patients with heart failure (HF) with NYHA functional class  $\geq$  II (according to 2021 EU guidelines).
- Patients over 18 years of age.

- Patients who have suffered acute HF decompensation (first and recurrent) in the 30 days prior to enrollment in the study.

*\*An acute decompensation of HF is defined as a new episode of symptoms and signs that requires intravenous decongestive treatment or increased oral diuretics either on an outpatient basis (e.g., day or home hospitalization for HF) or at home, emergency department or requiring an unplanned hospital admission.*

- NT-pro BNP  $\geq 300$  pg/ml at study inclusion for patients without ongoing atrial fibrillation/flutter. If ongoing atrial fibrillation/flutter, NT-pro BNP should be  $\geq 600$  pg/mL
- Patients must have had an echocardiogram during their HF hospitalization or in the previous 12 months.
- Before starting any procedure, the hospital will ensure that the patient obtains an informed consent document.
- All patients will be eligible regardless of LVEF level: HFrEF, HFmrEF and HFpEF.
- Patients with minimal skills in handling mobile applications.

### 7.2.2 Exclusion criteria

- Oncology patients with metastasis or ongoing chemotherapy treatment.
- Patients participating in other studies or trials.
- Patients who do not wish to participate.
- Patients weighing more than 150 kg.
- Patients who do not speak Catalan, Spanish, English, Portuguese, Italian, Dutch, German, Swedish, Hungarian, Romanian or French.
- Patients without a mobile phone.
- Patients without internet connection.
- Patients with moderate or severe cognitive impairment without a competent caregiver.
- Patients with severe psychiatric illness.
- Patients with planned cardiac surgery.
- Patients with planned heart transplant or LVAD implant.

### 7.2.3 Withdrawal criteria

Subjects will be informed that they can withdraw from the research whenever they wish, without this affecting in any way their subsequent medical care.

Complete withdrawal of consent for research means that the subject no longer wishes to use the investigational product and is unwilling or unable to continue participation in the research. Any subject may withdraw full consent to participate in the research at any time during the research. The investigator will discuss with the subject the most appropriate way to withdraw to ensure their health.

Every effort should be made to complete and report observations as widely as possible up to the date of withdrawal. All information must be included in the corresponding data collection notebooks.

The withdrawal criteria established for clinical research are as follows:

- Disease progression
- Withdrawal of consent or desire to terminate treatment or investigational product or failure to cooperate with research requirements
- Toxicity, adverse event, or intercurrent illnesses, in the opinion of the investigator, that justify discontinuation of treatment or investigational product
- Decision of the principal investigator, whether withdrawal is necessary to safeguard the interests of the patient
- Patient death
- New exclusion criteria clinically relevant to participants and affecting their safety
- Failure to comply with or significant deviation from the clinical research plan

If the participant withdraws from the study, their data will be automatically anonymized by the platform at the end of the study. This anonymization is not carried out if the participant gives explicit consent. The withdrawn participant will receive standard follow-up care designated by their respective medical professional.

## 7.3 Recruitment

After verifying that the selected subjects meet the inclusion and exclusion criteria, they will be offered to participate. A user ID (automatically generated on the HumanITcare platform) will be assigned to each subject who has given written informed consent to participate in the research. User IDs will not be reused for different participants. The investigator must maintain a selection/enrollment record of all selected subjects. This record must be carried out on a separate medium so that only the medical team at each center can relate the user ID to a specific subject.

The participant must personally sign and date the latest approved version of the informed consent form before performing any research-specific procedures.

Written and verbal versions of the patient information sheet and informed consent will be presented to participants, detailing, at a minimum, the following:

- The exact nature of the study

- The implications and limitations of the clinical research plan
- Known side effects and any risks involved with participation

It will be clearly indicated that the participant is free to withdraw from the research at any time and for any reason, without prejudice to future care, and without obligation to indicate the reason for withdrawal.

The participant will be given as much time as they wish to consider the information, and the opportunity to question the researcher to decide whether or not to participate in the study. Written informed consent will then be obtained by the participant's signature and the signature of the person who submitted and obtained informed consent.

### 7.3.1 Estimated recruitment time

Patients will be included in the study, based on the aforementioned eligibility criteria, for 3 months and will be monitored for 3 months. Each hospital will decide when to include their patients based on their particular clinical practice (either in the discharge planning process or during the first follow-up visit, i.e., approximately 1 week after discharge or after decompensation).

Medical professionals from each hospital will be in charge of recruiting participants. Patients will be recruited for 3 months.

Participants will be randomized in a 1:1 ratio to the control group (UC arm) or the intervention group (TM arm) at the recruitment stage. Randomization will be carried out at each center using the HumanITcare platform, which will indicate the arm to which each patient belongs. Stratification is performed with covariate adaptive randomization methods.

## 7.4 Investigation procedure

January - February 2023	Selection and coordination of partners. PIC Design Discussion
April 2023	CEIm Presentation
June 2023	CEIm approvals
November 2023	AEMPS approvals
November 2023	Start of the study. Register researchers on the platform. Start patient recruitment.
November 2023	First patient - first visit
January 2023	Last patient - first visit

January 2023	First patient - last visit
April 2023	Last patient - last visit
April 2023	Analysis of results. Draft version of the article

All patients included in the study will be followed for 3 months. The medical professionals responsible for the study will be responsible for including patients in the study following the inclusion criteria. They will explain the characteristics of the study to the patient and ask if they are willing to be included. The patient will sign the informed consent, which includes acceptance of the use of active and passive data. Once accepted, medical professionals will register the user on the platform, which will randomly assign them to the UC or TM arm, complete all required data on their sociodemographics and risk factors, and train them in the proper use of the application and the devices (in the TM case).

The particular clinical practice for the UC and TM arms is specified below:

- Day 0 until end of study: Medical professionals will track health questionnaire responses through the platform. Doctors will make a follow-up call in case of missing data.
- Day 0 until the end of the study: Medical professionals must report each hospital readmission, mortality or emergency visit for each patient, specifying its cause each time it occurs through the platform. If you cannot register the event now, you can register events later by specifying the corresponding date(s) and duration.
- Day 0 until the end of the study: Medical professionals are required to report each medication change through the platform, whether due to a decision derived from an alarm or derived from a clinical evaluation.
- Day 90 (3 months): Last follow-up visit and end of the study: The patient's follow-up will end 3 months after inclusion in the study (first hospital discharge). Patients must answer the European Heart Failure Self-Care Behavior Scale (EHFScB scale), Minnesota Questionnaire for People with Heart Failure (MLHF), Simplified Medication Adherence Questionnaire (SMAQ), Mobile Device Competency Questionnaire and the "System Usability Scale" (SUS). Medical professionals will change the patient's status to "finished" on the platform.
- Medical professionals will be asked to answer the PSSUQ questionnaire at the end of the entire study period.
- Medical professionals may schedule patients for more in-person visits depending on the specific clinical practice of each center.

### TM Arm Tracking

Patients in the TM arm will be followed with the HumanITcare platform and app according to the guidelines specified below.

- Day 0: First visit and study enrollment before or after hospital discharge for HF, or after acute decompensation. This first visit will include,
  - Explanation of the study to the patient and clarification of doubts
  - Explanation of the terms and conditions, and signing of the informed consent
  - Patients will be registered within the platform and the study group (UC or TM) will be automatically assigned from the software. In this case the TM.
  - Patients will receive a scale, blood pressure monitor, smartwatch and pulse oximeter. The devices will sync with the app (or the carrier's app in some cases). The patient must wear the smartwatch throughout the study period, charging its battery every time it is about to run out and putting it back on just when it is fully charged.
  - Registration of information on sociodemographic variables and patient risk factors on the platform by the medical professional.
  - Patients will answer the European Heart Failure Self-Care Behavior Scale (EHFScB scale), the Minnesota Questionnaire for People with Heart Failure (MLHF), and Mobile Device Proficiency questionnaires via the app.

- Day 0 until the end of the study: Recording of measurements and questionnaires: Patients will be notified through the app each time they need to record a measurement or answer a health questionnaire. Weight, blood pressure (systolic and diastolic), and oxygen saturation (via pulse oximeter) will be recorded daily. The times for each record are specified in the *Table 1*. Smartwatch device measurements are automatically recorded once synchronized with the application. The patients They must wear the smartwatch throughout the study period (except when it is being charged).
- Health questionnaires will be periodically delivered through the app to the patient. Specifically, the symptomatology questionnaire will be delivered twice a week (Monday and Thursday), self-care, quality of life and device competence questionnaires Mobile phones will be delivered once at the beginning and once at the end of the study, and the medication adherence questionnaire will be answered once every month during the study(see Table 1).
- Day 0 until end of study: Medical professionals will track patients' adherence to the study by verifying their measurements and health questionnaire responses through the platform. Doctors will make follow-up calls in case there is missing data.
- Day 0 to end of study: Medical professionals should note each alarm each time they receive it and verify its relevance. If they cannot evaluate it at the time of appearance, they are allowed to do so later. However, we recommend writing down alarms, if any, daily. Annotations will include adding information about the relevance of an alarm and evaluating the patient's health status.
- Day 0 until the end of the study: Medical professionals must report each hospital readmission, mortality or emergency visit for each patient, specifying its cause each time it occurs through the platform. If you cannot register the event now, you can register events later by specifying the corresponding date(s) and duration.
- Day 0 until the end of the study: Medical professionals are required to report each medication change through the platform, whether due to a decision derived from an alarm or derived from a clinical evaluation.
- Day 7 to 10: First follow-up visit: Medical professionals will schedule patients for an in-person follow-up visit depending on the particular clinical practice of each recruiting center.
- Day 90 (3 months): Last follow-up visit and end of the study: The patient's follow-up will end 3 months after inclusion in the study (first hospital discharge). Patients must answer the European Heart Failure Self-Care Behavior Scale (EHFScB scale), the Minnesota Questionnaire for People with Heart Failure (MLHF), the Mobile Device Competence Questionnaire and the "System Usability Scale" (SUS) . They will then be asked to return the medical devices and medical professionals will change the patient's status to "finished" on the platform.
- Medical professionals will be asked to answer the PSSUQ questionnaire at the end of the entire study period.
- Medical professionals may schedule patients for more in-person visits depending on the specific clinical practice of each center.

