TM + UC	Clinical events Hospital readmission Urgent visit with intravenous decongestant Emergency Department Visits Death	Number and dates	In the occurrence		Medical professionals through the platform
TM + UC	Questionnaires European Heart Failure Self-Care Behavior Scale (EHFScB scale) Minnesota Questionnaire for People with Heart Failure (MLHF)	From 0 to 100	2 times: when included in the study and at the end of the study at 3 months		Patients via app questionnaire
	Mobile Device Proficiency Quiz Simplified Medication Adherence Questionnaire (SMAQ)	From 8 to 40 from 0 to 4	3 times: when included in the study and once a month		

The questionnaires given to patients are specified below and added in Annex 1:

- Minnesota Questionnaire for People with Heart Failure (MLHF) (Garin et al., 2008)
- European Heart Failure Self-Care Behavior Scale (EHFScB scale) (Jaarsma et al., 2009)

- Symptom Report Questionnaire: six questions to capture worsening heart disease symptoms, primarily worsening HF, and one question to capture overall deterioration.
- The “System Usability Scale” (SUS) (Brooke, 1995) and the “Post Study Usability Questionnaire” (PSSUQ) (Lewis, 1992) They will be delivered at the end of the study.
- Mobile Device Proficiency Questionnaire (MDPQ) (Roque & Boot, 2018)
- Simplified Medication Adherence Questionnaire (SMAQ) (Ortega Suárez et al., 2011)

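### All four readmission and emergency-visit endpoints rest on a cause label entered by staff who know the arm; defined all-cause counts could be added from data already recorded

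*Combined protocol and SAP*

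**What the plan says.** **Endpoints.** Section 7.1.3 lists four secondary endpoints for readmissions and emergency visits. One readmission endpoint is limited to HF: "Hospital readmission due to HF decompensation (Total number of hospitalizations in 3 months". A second has the same form but takes any CV cause. Emergency visits follow the same pattern. The HF version reads "Visits to the emergency room due to HF decompensation (Total number of visits to the emergency room in 3 months", and its companion is again restricted to CV causes.

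Death is treated differently. It has a CV version and also an any-cause version: "Mortality from any cause (Total number of patients who died in 3 months".

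**Who assigns the cause.** Section 7.4 (TM Arm Tracking) states: "Medical professionals must report each hospital readmission, mortality or emergency visit for each patient, specifying its cause each time it occurs through the platform". The usual-care (UC) subsection gives the same rule.

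**Knowledge of the arm.** Section 7.3.1 says: "Randomization will be carried out at each center using the HumanITcare platform, which will indicate the arm to which each patient belongs". In TM, the medical professionals also review measurements and annotate alarms.

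**What is recorded.** Table 1 in section 9.1 has one block for both arms, "Clinical events Hospital readmission Urgent visit with intravenous decongestant Emergency Department Visits Death", collected as number and dates when they occur.

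**Analysis and objective.** Section 8.1 compares readmission counts and hospital days between arms by a Wilcoxon rank sum test and names no cause. The secondary objective in 6.2 concerns fewer readmissions, also with no cause limit.

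**The concern.** Whether a readmission of a patient with HF is put down to HF, to another CV problem or to something else is often a judgement. Here it is made by people who know the allocation, with different information in each arm. TM staff have daily weight, blood pressure and saturation, and symptom reports twice a week. UC patients have no devices, and Table 1 collects symptoms in TM only.

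The direction of any resulting bias cannot be predicted. Richer data could make TM staff apply the HF label more often. A belief that monitoring prevents decompensation could make them apply it less often. Either would move the HF counts with no change in how often patients return to hospital.

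A count of all readmissions, or of all emergency visits, does not depend on the label. For readmissions, the plan leaves unclear whether such a count is meant. For emergency visits, it has none.

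**Working it through.** **1. Compare the endpoint list with the data collected.**

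| Event | Recorded in both arms whatever the cause (7.4, Table 1) | Cause-specific endpoint (7.1.3) | All-cause endpoint (7.1.3) | Count comparison in 8.1 |
|---|---|---|---|---|
| Death | yes | CV | yes | – |
| Readmission | yes | HF, CV | none | yes, cause not stated |
| Emergency visit | yes | HF, CV | none | none |

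So 4 of 4 readmission and emergency-visit endpoints are cause-specific and 0 are all-cause, while the data for all-cause counts are already collected.

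**2. Look for safeguards on the label.** Section 7.1.3 defines acute HF decompensation, but partly through increased oral diuretics, which is itself a clinician's decision. I found no rule for choosing among HF, other CV and non-CV when several causes apply. Under 7.5 the monitor compares the case report form with source data. Under 9.1 the source documents are the doctor's patient records. That checks transcription; it is not a blinded reading of cause.

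**3. Size, by illustration.** The plan gives no event rate and no figure for these endpoints, so there is nothing of its own to reproduce. Its total of 253 (7.1.4) is based on the Minnesota questionnaire (MLHF).

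Inputs:
- n = 253/2 = 126.5 per arm, from 7.1.4 and 1:1 allocation.
- Assumed: r = 0.2–0.4 readmissions per patient in 3 months; share due to HF, s = 0.4–0.6; share of TM HF readmissions coded to another cause, m = 0.10–0.20; no true effect.

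Formulas:
- UC HF count = n·r·s; TM HF count = n·r·s·(1 − m).
- Apparent HF ratio = 1 − m, whatever n, r and s are.
- All-cause count = n·r in each arm, so the ratio is 1.00.
- If TM staff apply the HF label more often by a share m, the HF ratio is 1 + m and the all-cause ratio is still 1.00.

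Example with r = 0.3, s = 0.4: UC HF = 126.5 × 0.3 × 0.4 = 15.2.

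| m | TM HF count | HF ratio | All-cause count per arm | All-cause ratio |
|---|---|---|---|---|
| 0.10 | 13.7 | 0.90 | 126.5 × 0.3 = 38.0 | 1.00 |
| 0.20 | 12.1 | 0.80 | 38.0 | 1.00 |

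The same shares of over-labelling give HF ratios of 1.10 and 1.20.

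**4. Would this alone produce a significant result?** Seldom. I treated the HF rates as proportions of patients and used the normal approximation for a two-sided 5% test. Over the ranges above, the chance of a significant result favouring TM is 4.3–6.6% at m = 0.10 and 7.1–15.1% at m = 0.20, against 2.5% with no mislabelling. The main effect is on the estimate.

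**5. Should agreement in direction between HF and all-cause counts be required?** I simulated Poisson counts with 126 per arm and the same r and s.
- No true effect, m = 0.10–0.20: when the HF count favours TM, the all-cause count also favours TM in about 59–70% of cases. Most spurious results would pass.
- True HF rate ratio 0.80, no mislabelling, no effect on other causes: the all-cause count fails to favour TM in about 16–26% of the cases where the HF count does.

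Such a rule screens poorly and blocks some real effects.

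**6. Cost of dilution.** With a true HF ratio of 0.80 and no other effect, the all-cause ratio is 1 − 0.20·s, that is 0.92 at s = 0.4 and 0.88 at s = 0.6.

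**The case against.** **Section 8.1 may already contain the all-cause comparison.** It names no cause, and neither does the objective in 6.2. A reader might infer that the plan offers no all-cause readmission comparison at all; the documents do not support that. What stands is that no listed endpoint defines the count, so which readmissions enter the test could be settled after the data are seen. Emergency visits are not in that sentence.

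**Other outcomes offer a partial check.** A reader might also infer that nothing in the plan could expose mislabelling. That is too strong. An HF event relabelled as another CV event stays in the CV counts, and medical care costs cover hospitalization and emergency care with no cause limit. Neither is a defined all-cause event count, and an event moved to a non-CV cause leaves both the HF and the CV counts.

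**All-cause counts are not free of bias.** This is correct. Staff who know the arm may influence whether a patient is admitted or sent to the emergency room. Late entry of events is allowed, and TM patients are watched more closely, so capture could also differ.

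**Cause-specific outcomes are a legitimate choice in an HF trial, and these are secondary.** Also correct. The primary endpoint is a questionnaire composite and is untouched, as is the sample size.

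**The relabelling shares are assumed.** They are. The arithmetic follows from them, but nothing in the documents supports the range or the direction.

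**Conclusion.** The point holds as a cheap improvement. All four readmission and emergency-visit endpoints depend on a cause entered by staff who know the arm and have more information in TM; no blinded adjudication is described. The documents never use the word unblinded; I infer it from the allocation and alarm procedures. The readmission comparison in 8.1 needs its scope stated, and an all-cause emergency-visit count is missing although the events are recorded.

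The figures (HF ratio 0.80–0.90 or 1.10–1.20 with no true effect) illustrate an assumed 10–20% difference in labelling and are not estimates of what will happen. They apply to the HF endpoints. The CV endpoints would move less where events shift only between HF and other CV causes.

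A reader might conclude that all-cause counts would cure the effects of open-label care. They would not: they remove bias from cause attribution only.

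**What to change.** - In 7.1.3, add all-cause hospital readmissions and all-cause emergency visits, each as a total count to Day 90.
- In 8.1, state that the readmission count to be compared is the all-cause count, and name a comparison for all-cause emergency visits.
- Report both beside the HF and CV versions, and discuss any discordance when interpreting the cause-specific results. Do not require the two to agree in direction.
- State in the report that the all-cause counts do not address unblinded decisions to admit or unequal event capture.

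**Cost.** Two endpoint lines, a clarification in 8.1 and a little analysis; no new data, no assessors and no change to 253. The list of secondary endpoints grows from eleven to thirteen. All-cause counts dilute an HF-specific effect, so the cause-specific endpoints should stay.
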